5. STATISTICAL CONSIDERATIONS

A. Sample size

As a single-arm study designed to provide normative results for the lens, there is no relevant sample size calculation. Some subgroup analysis is desirable (e.g., toric vs. non-toric, photopic vs. mesopic results, differences by surgeon and/or site). It is expected that 100 subjects (200 eyes) will be sufficient to allow this type of subgroup analysis.

B. Statistical Analysis

All data will be collected by each site and entered into a database. Subjects will be assigned an ID number. Data analysis will be performed without patient identification. Statistical analysis will be performed using standard descriptive statistics and other tests as deemed appropriate based on the characteristics of the data to be analyzed. All statistical tests will be two-sided and interpreted at a 5% significance level. Data analysis will be conducted by a third-party consultant.

C. Study Endpoints:

1. Primary Endpoints:

1. Binocular distance corrected near visual acuity at 40 cm under photopic conditions
2. Binocular distance corrected near visual acuity at 40 cm mesopic conditions

2. Secondary Endpoints:

1. Binocular low contrast distance visual acuity under photopic and mesopic conditions
2. Uncorrected and distance-corrected near (40 cm) visual acuity
3. Uncorrected and distance-corrected intermediate (66 cm) visual acuity
4. Uncorrected and best-corrected distance (4 m) visual acuity
5. Distance-corrected near visual acuity at best distance
6. Non-directed complaints
7. To evaluate patient's overall satisfaction of their vision
8. To evaluate patient's spectacle independence
9. To evaluate visual symptoms using a questionnaire
10. To evaluate the functional vision questionnaire
11. Residual mean spherical equivalent refraction
12. Residual refractive sphere
13. Residual refractive cylinder
14. Percentage of eyes with postoperative MRSE accuracy to target $\leq 0.5D$

D. Safety Analyses

The type, severity, duration and frequency of reported ocular adverse events will be tabulated. Adverse events will also be summarized for events that were considered treatment-related. Comparison of treatment groups with respect to the proportion of study patients reporting adverse events will be made using Fisher's Exact Test.

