The TECNIS Synergy IOL is a one-piece presbyopia-correcting IOL available in non-toric and toric versions that was introduced to the US market in June 2021. At our center, we were the first site in the US to implant the Synergy (June 7, 2021) and have been using the IOL ever since. This Synergy IOL is part of the TECNIS platform, which is composed of time-tested hydrophobic acrylic material with ultraviolet and violet light absorber, 6-mm aspheric optic, refractive index of 1.47, and continuous 360 ° posterior square edge design. The company boasts that the new Synergy IOL combines the benefits from the TECNIS Multifocal and TECNIS Symfony (EDOF) diffractive designs, and that it delivers a wider range of continuous vision and better near vision in day and night than a leading trifocal IOL.¹

To date, there have been only a few investigator-initiated studies that have evaluated the clinical outcomes of the Synergy, but none of these studies have been US-based, nor have they featured a large number of subjects.²⁻⁴

We propose conducting a prospective evaluation of Synergy outcomes that will feature our first 7 months of data collected at our two high-volume, US-based cataract practices. We expect that this analysis will be the first of its kind and will be useful for US cataract surgeons who are considering implementing the Synergy lens in their practice.

1. OBJECTIVE:

To evaluate the visual outcomes in patients with and without astigmatism who underwent uneventful phacoemulsification and bilateral implantation of the TECNIS Synergy IOL.

2. STUDY DESIGN AND METHODS:

- A. **Test article:** Tecnis Synergy Intraocular lens Toric (DFWXXX) and non-toric (DFR00V) using TECNIS Simplicity Delivery System
- B. **Study Design:** Ambispective, multicenter (up to 2 sites in USA), non-therapeutic, single-visit study.
- C. **Subjects:** All consecutive patients who underwent uneventful routine femtosecond assisted laser lens removal and implantation of the Synergy IOL between June 01, 2021 and December 31, 2021 (up to 100 patients) who meet the Inclusion/Exclusion criteria will be enrolled.

1. Inclusion Criteria:

Subjects **MUST** fulfill the following conditions to qualify for enrollment into the trial

1. Age: 18 years and older.
2. Gender: Males and Females.
3. Uneventful bilateral, femtosecond laser assisted lens extraction

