4. Bilateral implantation of Synergy IOLs (toric and non-toric) by 5 anterior segment surgeons at Center For Sight ([name], [name], [name], [name], and [name]) and 1 surgeon at Carolina EyeCare Physicians ([name]) through the months of June to December 2021.
5. Willing and able to provide written informed consent for participation in the study.
6. Willing and able to comply with scheduled visit and study examination procedures.
7. Available Macular OCT, IOLMaster700, and Pentacam obtained preoperatively.
8. At least 3 months postoperative from second eye IOL implantation.
9. Postoperative best corrected visual acuity of 0.2 logMAR (20/32 Snellen) or better in both eyes.

2. Exclusion Criteria:

Subjects with **ANY** of the following conditions on the eligibility exam may **NOT** be enrolled into the trial.

1. Established ocular pathology, including: glaucoma (except glaucoma suspects), uveitis, and clinically-significant retinal pathology affecting the macula (with visual acuity worse than 20/32) and/or any other ocular findings that may, in the opinion of the investigator, affect vision.
2. Uncontrolled diabetes.
3. Use of any systemic or topical drug known to interfere with visual performance.
4. Any concurrent infectious/non-infectious conjunctivitis, keratitis or uveitis.
5. Clinically significant corneal dystrophy.
6. Irregular astigmatism.
7. History of chronic intraocular inflammation.
8. Previous intraocular surgery.
9. Previous keratoplasty
10. Previous refractive surgery.
11. Severe dry eye
12. Pupil abnormalities
13. Any clinically significant, serious or severe medical or psychiatric condition that may interfere with the interpretation of study results.
14. Participation in (or current participation) any ophthalmic investigational drug or ophthalmic device trial within the previous 30 days prior to the start date of this trial.
15. Best-corrected distance visual acuity worse than 20/32 in each eye.
16. Inability to focus or fixate for prolonged periods of time (e.g., due to strabismus, nystagmus, etc.)
17. Abnormal iris
18. Patients who had a complication during cataract surgery, which could include ruptured zonules, torn capsule, or vitrectomy.

The principal investigator reserves the right to declare a patient ineligible or non-evaluable based on medical evidence that indicates the patient is unsuitable for the trial.

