Reading speed at 40 cm under photopic conditions	X**
Reading speed at 40 cm under mesopic conditions	X**
Pupil size under photopic conditions	X
Pupil size under mesopic conditions	X
SLE	X
Dilated fundus exam	X [‡]
Preoperative data (Macular OCT, IOL Master700 and Pentacam)	X [¥]
Intraoperative data (IOL type, IOL power, target refraction, formula used to calculate IOL power, if toric IOL, final axis placement, estimated residual astigmatism and axis)	X
PCO evaluation	X
Toric IOL position	X [‡]
Questionnaires and non-directed complaints	X
AE/Device deficiencies	X

X To be performed as scheduled

* Monocular and binocular testing

** Binocular testing only

[‡] To be performed as deemed necessary by the investigator.

[¥]If available

4. Study endpoint criteria

- A. Patient Completion of Study: If a study patient has completed the study visit, he/she is considered to have completed the study.
- B. Study Completion: The study will be complete when all subjects are enrolled and have completed the study visit.

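### Does the toric versus non-toric comparison need a written rule for patients with one lens of each type, and for paired eyes?

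*Combined protocol and SAP*

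**What the plan says.** The objective (section 1) is worded by patient: "To evaluate the visual outcomes in patients with and without astigmatism". Inclusion criterion 4 asks for "Bilateral implantation of Synergy IOLs (toric and non-toric) by 5 anterior segment surgeons" at one centre and one surgeon at the other. It does not ask for the same version in both eyes.

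The two primary endpoints (section 5.C.1) are "Binocular distance corrected near visual acuity at 40 cm under photopic conditions" and "Binocular distance corrected near visual acuity at 40 cm mesopic conditions". Table 1 marks near, intermediate and low-contrast acuity as "Binocular testing only". Distance acuity at 4 m is tested both ways. The surgical data in Table 1 include lens type, power and, "if toric IOL, final axis placement, estimated residual astigmatism and axis". These are attributes of a single eye, although the table does not use the words per eye.

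Section 5.A describes a single-arm study meant to give normative results, offers no sample size calculation, and adds: "Some subgroup analysis is desirable (e.g., toric vs. non-toric, photopic vs. mesopic results, differences by surgeon and/or site". It expects 100 subjects (200 eyes) to be enough. On method, section 5.B says: "Statistical analysis will be performed using standard descriptive statistics and other tests as deemed appropriate based on the characteristics of the data". Tests are two-sided at 5%, and a third-party consultant runs them. Section 5.D compares adverse event proportions between treatment groups that it does not define, and section 8.C marks assignment to groups as not applicable.

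**The concern.** The first subgroup comparison named in section 5.A splits on an eye-level attribute, but the primary endpoints exist only at patient level. A patient with a toric lens in one eye and a non-toric lens in the other fits neither group. An analyst could drop such patients, count them as toric, or count them as non-toric. Each choice gives different groups and, if the lens versions truly differ, a different estimate. With no rule written down, the choice could be made after seeing results. The same question would arise for surgeon if two surgeons shared a patient, and for the safety comparison if its groups are meant to be the two lens versions.

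Separately, secondary endpoints 11 to 14 (residual refraction and accuracy to target) are eye-level by nature, with two eyes per patient. Nothing in section 5 says that a test or interval will allow for that pairing. Treating 200 eyes as independent would make tests between patient groups too liberal.

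**Working it through.** **The plan's own figure.** 100 patients × 2 = 200 eyes, which agrees. The statement that this is enough for subgroup work has no stated power, effect size or SD behind it, so it cannot be reproduced.

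**Inputs that must be assumed.** None of the following is in the documents: share of toric eyes q (0.3 to 0.5), between-eye correlation of lens version φ (0.2 to 0.8), position w of mixed patients between both-non-toric (0) and both-toric (1), the both-toric minus both-non-toric difference D, and the between-eye correlation of an outcome (ICC, 0.1 to 0.7).

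**How many mixed patients.** Mixed share = 2q(1−q)(1−φ); both toric = q − mixed/2; both non-toric = 1 − q − mixed/2.
- q = 0.3, φ = 0.8: 2 × 0.3 × 0.7 × 0.2 = 8.4%
- q = 0.4, φ = 0.5: 2 × 0.4 × 0.6 × 0.5 = 24%, so 28 / 24 / 48 patients (central case)
- q = 0.5, φ = 0.2: 2 × 0.5 × 0.5 × 0.8 = 40%
- q = 0.3, φ = 0.2: 2 × 0.3 × 0.7 × 0.8 = 33.6%, so about 13 / 34 / 53 patients

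**What each rule estimates (central case).** Dropping mixed patients gives D. Toric if either eye gives D × (28 + 24w)/52. Toric only if both eyes gives D × (1 − 24w/72).

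| w | drop mixed (28 v 48) | either eye (52 v 48) | both eyes (28 v 72) |
|---|---|---|---|
| 0 | 1.00 D | 0.54 D | 1.00 D |
| 0.5 | 1.00 D | 0.77 D | 0.83 D |
| 1 | 1.00 D | 1.00 D | 0.67 D |

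Every entry is a multiple of D. If D = 0, all three rules estimate zero.

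**How often the rules disagree at p < 0.05 (central case, simulated t-tests).** The ranges run over w = 0, 0.5 and 1.
- D = 0.6 SD: about 31 to 47% of studies
- D = 0.2 SD: about 15 to 17%
- D = 0: about 8%. At least one of the three rules is significant in about 9%, which matters only if someone tries all three and reports the best.

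**What separating mixed patients costs.** Detectable difference at 80% power, two-sided 5%, two-sample t-test. The normal approximation, 2.80 × √(1/n₁ + 1/n₂), gives 0.56, 0.67 and 0.87 SD for the three rows; the t-test values are slightly larger.
- Either-eye rule, 52 v 48: 0.57 SD
- Mixed set aside, 28 v 48: 0.68 SD
- Mixed set aside, 13 v 53: 0.88 SD, against 0.57 SD for the either-eye rule (47 v 53) in the same population

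**Paired eyes.** With both eyes in the same group, the variance inflation is 1 + ICC. A test that ignores it has true level 2 × (1 − Φ(1.96/√(1 + ICC))): 6.2%, 8.6%, 11.0% and 13.3% at ICC 0.1, 0.3, 0.5 and 0.7. For an eye-level toric contrast on a mean, the inflation is 1 + ICC × φ, giving 5.2% (ICC 0.1, φ 0.2) to 11.7% (ICC 0.7, φ 0.8). Means and percentages over eyes do not change. Section 5 specifies no test on endpoints 11 to 14, so these figures describe a mistake the plan does not direct anyone to make.

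**The case for a change.** The case for a change is that freedom to choose a test is not the same as a definition of groups. Section 5.B supplies the first and no section supplies the second. Section 5.A uses subgroup work to support 100 patients, section 5.B applies a 5% level to every test, and section 12 plans publication, so the comparison may well be reported with a p-value. A rule would take a few sentences, and because the lenses are already implanted, mixed patients can be counted from surgical records.

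Much of this stands. The documents contain no grouping or fellow-eye rule, and writing one down would do no harm. What does not stand is that the plan goes wrong without it. Nothing shows that any mixed patient exists. The documents give no reason to expect a lens-version difference on the primary endpoints, which are measured with distance correction in place, and D = 0.6 SD is an assumption close to the detectable limit, where rules disagree most. More than one rule would be acceptable, and keeping mixed patients apart has a real price in precision. The surgeon version of the point is more speculative still. The undefined safety groups are a matter of defining a term; only if they mean the two lens versions do they bear on this question.

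**Conclusion.** No change is needed. This is unfilled detail in an optional, exploratory comparison, and a competent analyst working under section 5.B would settle it: count the mixed patients, state how they were grouped, and allow for two eyes per patient wherever eyes are the unit. The normative results for all patients, which are the purpose of the study, are the same under every grouping rule, and no stated figure or rule is shown to be wrong.

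The possible effect is bounded but cannot be fixed from the documents. In the assumed central case the alternative rules give 0.54 to 1.00 times D, and nothing at all turns on the rule if no patient is mixed. Inflation to between 6.2% and 13.3% on mean refraction would arise only if pairing were ignored, at assumed ICCs of 0.1 to 0.7. Against that, the most natural explicit rule moves the detectable difference from 0.57 SD to between 0.68 and 0.88 SD in the two compositions worked through. Reporting the number of mixed patients beside any toric versus non-toric result would let readers judge it.

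### The only endpoint that compares achieved with intended refraction is a within-0.5 D percentage; signed and absolute error from target should be reported too

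*Combined protocol and SAP*

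**What the plan says.** The secondary endpoints in Section 5.C contain four refractive items. Item 11 is "Residual mean spherical equivalent refraction", items 12 and 13 are residual sphere and residual cylinder, and item 14 is "Percentage of eyes with postoperative MRSE accuracy to target" with a limit of 0.5 D. Only item 14 refers to the target. No mean signed or mean absolute error from target is listed.

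The inputs for such an error are collected. Manifest refraction is measured at the study visit, and Table 1 lists "Intraoperative data (IOL type, IOL power, target refraction, formula used to calculate IOL power" among the surgical data.

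On group comparisons, Section 5.A says "Some subgroup analysis is desirable (e.g., toric vs. non-toric, photopic vs. mesopic results, differences by surgeon and/or site" and adds "It is expected that 100 subjects (200 eyes) will be sufficient to allow this type of subgroup analysis". It also says that "there is no relevant sample size calculation". Section 5.B says "All statistical tests will be two-sided and interpreted at a 5% significance level", but otherwise leaves the choice of method open. The only test named anywhere is Fisher's exact test, for adverse events.

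**The concern.** The error of interest is achieved minus target spherical equivalent, a signed quantity in dioptres. Item 14 cuts it at 0.5 D, read here as applying in both directions; the plan does not write this out, but it is the natural reading. After the cut, a miss of 0.1 D counts the same as one of 0.5 D, and 0.6 D the same as 2 D. A myopic miss counts the same as a hyperopic miss of equal size.

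Item 11 keeps size and sign but measures the residual refraction itself. It equals the error plus whatever the surgeon intended. The inclusion criteria name six surgeons at two sites, and target and formula are recorded as data items rather than fixed by the protocol. If mean targets differ by surgeon, site or lens type, a difference in item 11 may reflect intention, error or both.

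At stake is whether a study meant to supply reference results for this lens can say how far, and in which direction, eyes land from target, and whether the comparisons in Section 5.A can address that directly.

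**Working it through.** The plan states no power, SD or group sizes, so there is no figure of its own to reproduce.

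**From the plan:** 100 subjects (200 eyes); two-sided 5% level; limit 0.5 D.

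**Assumed:** error normal with mean m and SD s; s = 0.30, 0.40 or 0.50 D; groups of 50 and 50; one value per patient; one group on target, the other 0.20 D off.

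**Item 14.** Pass rate = Φ((0.5 − m)/s) − Φ((−0.5 − m)/s). At s = 0.40 this is 78.9% for m = 0 and 73.3% for m = 0.20. The standard error of the difference is √(0.789×0.211/50 + 0.733×0.267/50) = 0.085, so z = 0.055/0.085 = 0.65. Power is Φ(0.65 − 1.96) + Φ(−0.65 − 1.96), about 10%.

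**Signed error.** The two-sample t-test has non-centrality 0.20/(0.40 × √(2/50)) = 2.50 on 98 degrees of freedom, giving power of about 70%.

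| SD of error (D) | Pass rates | Power, item 14 | Power, signed error |
|---|---|---|---|
| 0.30 | 90.4% vs 83.2% | 19% | 91% |
| 0.40 | 78.9% vs 73.3% | 10% | 70% |
| 0.50 | 68.3% vs 64.5% | 7% | 51% |

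With a 30/70 split at SD 0.40, the powers are 9% and 62%.

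**Item 11.** If the target has SD τ within groups, is independent of the error and has the same mean in both groups, the SD of residual spherical equivalent is √(0.40² + τ²).

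| τ (D) | SD of item 11 (D) | Non-centrality | Power |
|---|---|---|---|
| 0 | 0.400 | 2.50 | 70% |
| 0.1 | 0.412 | 2.43 | 67% |
| 0.2 | 0.447 | 2.24 | 60% |
| 0.3 | 0.500 | 2.00 | 51% |

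**Offset straddling target.** With groups at +0.10 and −0.10 D and SD 0.40, both pass rates are 77.5%. Item 14 then has power equal to its 5% significance level. Signed error keeps 70%, because the difference is still 0.20 D, and item 11 keeps the powers in the table above.

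**Unequal mean targets.** Suppose both groups hit their targets on average, but one aimed 0.20 D differently. The same arithmetic applies to item 11: it shows a significant difference in 60% to 70% of trials (τ from 0.2 to 0 D) although neither group has an offset from target. If the difference in aim and a real error cancel, item 11 shows nothing.

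**Spread only.** With both groups on target and SDs of 0.30 and 0.45 D, simulation with 50 per group gives power of 63% on the cut and about 75% on absolute error.

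**Counting eyes.** With 200 eyes and an assumed fellow-eye correlation of 0.5, the effective number is 200/1.5 = 133, or about 67 per group. For 0 vs 0.25 D, item 14 (pooled two-proportion test) has power of about 44%, 20% and 10% at SD 0.30, 0.40 and 0.50. Signed error has 99.8%, 95% and 82%. The contrast does not depend on using one value per patient.

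**The case against.** A reader might infer that an offset between lens types, surgeons or sites would be almost invisible to the planned analysis. The documents do not support that, for three reasons.

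- Item 11 is already in the plan. With equal mean targets, the between-group difference in item 11 is the between-group difference in signed error. In the 0.20 D example the plan as a whole therefore offers 51% to 70%, not 10%. With a near-uniform target, its mean would also show whether eyes land myopic or hyperopic of target.
- No test of item 14 is planned. The study is single-arm and descriptive, subgroup comparisons are only called desirable, and the open wording of Section 5.B would let the analyst summarise signed error anyway.
- Item 14 is not blind to larger one-sided offsets. At 0 vs 0.50 D with 50 per group, the same formula gives pass rates of 78.9% vs 49.4% and power of about 90% at SD 0.40; it is about 57% at SD 0.50 and nearly 100% at SD 0.30.

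All three points stand, and they limit the finding. They do not remove it. Item 11 stands in for error from target only if mean targets are alike, which the documents neither state nor exclude, and it gives no absolute error. Permission to compute signed error is not a commitment to report it.

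**Conclusion.** The concern holds in a narrow form. Error from target appears in the plan only as a 0.5 D pass/fail percentage, which discards size and sign. Item 11 partly covers the gap when mean targets are alike, but it mixes error with intention when they are not.

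For a 0.20 D one-sided offset at SD 0.40, power is about 10% on item 14, 51% to 70% on item 11 and 70% on signed error. For an offset symmetric about target, item 14 has 5%. These figures rest on assumed SDs, offsets and an even split with one value per patient. The item 11 range also assumes equal mean targets. Comparisons among six surgeons would involve smaller groups and less power on any measure.

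The importance is minor. Item 14 is one of 14 secondary endpoints, and both primary endpoints are distance-corrected, so a refractive offset affects them little.

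**What to change.** Reword item 14 along these lines: MRSE error relative to target (achieved minus target, in D), reported as mean signed error and mean absolute error with 95% confidence intervals, overall and by lens type, surgeon and site, using a method that accounts for two eyes per patient, such as a mixed model or GEE. The percentage of eyes within 0.5 D of target is kept as a descriptive summary. Any between-group test of accuracy to target is based on the continuous error.

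The cost is one endpoint sentence, two more summary lines and a model that handles paired eyes. No new data, visits or patients are needed, and keeping the percentage preserves comparison with studies that report it. Making the change before analysis also narrows the choice that Section 5.B leaves open.

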6. DATA HANDLING AND RECORD KEEPING

A. Confidentiality

To ensure confidentiality in this study, records of the participants will be examined only by the principal investigator, sub-investigator(s) and research staff involved in the study. Study records will be kept on file at each site. Any statistical analysis and publication will not include any subject identifiers. Medical records will be made available only for review by the investigators, study

Monitor or Auditor, Sponsor Company or Research Institution, the IRB, and other State or Federal Regulatory Agencies, if necessary. All information in these records will be kept confidential.

B. Records Retention

The PI is accountable for the integrity, retention and security of all study related data. The investigator must maintain accurate, complete and current records relating to the clinical study. The investigator must maintain the required records during the investigation and for a period of 3 years after the date on which the investigation is terminated or completed.

